5.2.4. Post-treatment follow up

All study subjects who received at least one dose of FMP will be followed by telephone to assess adverse events and disease status for a total of 6 months after their last FMT dose. Subjects will be contacted by phone weekly for the 1st month and then monthly for the following 5 months and will have stool sample collection and medical examination at 3 months and 6 months after their last dose.

5.2.5. End of Study or Early Termination Visit

If withdrawing early from the study for any reason, subjects will be invited to come in for a final visit to provide a stool sample and routine labs (if indicated).

Follow-up for subjects who signed the consent form, but did not complete the study (**does not include screen failures**) is as followed:

- Active (full follow-up schedule) if subject received at least one dose of FMP IP.
- Active-abbreviated (Subjects will be called weekly for one month and then once at the second month for a total of two months), for subjects that received at least one dose of antibiotics and/or placebo IP but did not complete blinded treatment period or receive any FMP.

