4.1.4. Blinding and Randomization

The first ten eligible subjects will be randomized in a 1:1 ratio according to a pre-determined block randomization procedure to receive either FMT or placebo. If safety allows, the remaining cohort of 50 eligible subjects will be randomized in a 1:1 ratio according to a pre-determined block randomization procedure to receive either FMT or placebo. An unblinded pharmacist or delegate will maintain the randomization list ensuring subjects are randomized appropriately and dispensed the correct treatment. The investigator, research personnel and study subjects will be blinded to treatment assignments.

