6. SAFETY ASSESSMENT

6.1. Adverse Event Assessment and Reporting

Comprehensive assessments of any apparent adverse event(s) (AE) experienced by the study subject will be performed throughout the course of the study.

The PI will submit reports of unexpected Serious adverse events (SAEs) and other unanticipated problems to the Institutional Review Board (IRB) at Boston Children's Hospital and to OpenBiome according to their policies.

The PI will report events that are both serious and unexpected and that are associated with FMT/study intervention to the FDA and other applicable health authorities within the required timelines as specified in 21 CFR 312.32 (IND Safety Reports).

The following unexpected AEs will be assessed, recorded and reported to the Data Safety Monitoring Board (DSMB) on an expedited basis: all SAEs, AEs grade 3 (according to CTCAE 5.0 (31) if applicable) or above, and any unexpected AEs grade 2 or above that is possibly or probably related to FMT (as determined by a blinded investigator). Only an AE that meets the above criteria will be recorded and reported. Each reported AE will be described by its duration (i.e., start and end dates), regulatory seriousness criteria if applicable, expectedness, suspected relationship to the study treatment, and actions taken (a blinded investigator will determine expectedness, severity and relationship to study treatment).

Individual subject participation will be temporarily halted until the DSMB determines appropriateness of re-initiation of therapy in any subject experiencing an adverse event resulting in: an Emergency Department visit that is possibly or probably related to FMT, significant worsening of their disease, or experiences 1 SAE Grade \geq 3.

Individual subject participation in the study will be permanently stopped if a SAE Grade ≥ 3 is deemed possibly or probably related to FMT, including any hospital admission.

If 2 or more subjects experience 1 SAE grade \geq 4, all study activities will be halted until the DSMB determines appropriateness of re-initiation of therapy in any subject.

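### For subjects who leave after the first enema, follow-up length is set by the product received, which discloses the arm from about month 3 and gives FMT leavers 6 months against 2 for placebo

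*Combined protocol and SAP*

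**What the plan says.** Section 5.2.5 defines two follow-up tracks for consented subjects who are not screen failures and do not complete the study.

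- Full track: "Active (full follow-up schedule) if subject received at least one dose of FMP IP". Section 5.2.4 gives its content. It lasts "for a total of 6 months after their last FMT dose", and "Subjects will be contacted by phone weekly for the 1st month and then monthly for the following 5 months", with stool collection and a medical examination at months 3 and 6. Footnote 12 to the schedule in Section 5.1 uses the same criterion.
- Abbreviated track: "Subjects will be called weekly for one month and then once at the second month for a total of two months". It is meant "for subjects that received at least one dose of antibiotics and/or placebo IP but did not complete blinded treatment period or receive any FMP".

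On blinding, Section 4.1.4 states: "The investigator, research personnel and study subjects will be blinded to treatment assignments". Section 6.1 adds that "a blinded investigator will determine expectedness, severity and relationship to study treatment". The only unblinding described is in Section 5.2.3, after the last blinded dose at week 8.

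**The concern.** Once a subject has had the first enema, the two tracks are separated by one fact: whether the product was FMT or placebo. People who are meant not to know that fact must apply the rule, and the plan gives no mechanism for doing so.

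Two things are at stake.

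- **Blinding of late event judgments.** From the point where the tracks diverge, a continuing contact means FMT and silence means placebo. Whoever grades or attributes an event after that point may know the arm. Section 6.1 makes this consequential, because an unexpected grade 2 event is recorded only if it is judged possibly or probably related.
- **Unequal observation.** Section 7.3 keeps in the primary analysis everyone eligible and randomized who took at least one dose, so early leavers count. If the outcome runs over the whole study period, as Section 7.1 words it, leavers in one arm are observed for longer than leavers in the other.

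**Working it through.** **1. Who is affected.** Apply the Section 5.2.5 criteria by time of leaving:

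| Time of leaving | FMT arm | Placebo arm | Arm inferable? |
|---|---|---|---|
| Conditioning, Day -8 to -1 | antibiotics only: abbreviated | placebo antibiotics only: abbreviated | No |
| After first enema, before week-8 unblinding | has had FMP: full | no FMP: abbreviated | Yes |
| After week-8 unblinding | already unblinded (5.2.3) | already unblinded (5.2.3) | Not at issue |

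**2. When the arm shows.** Full track: 4 weekly contacts, then months 2, 3, 4, 5 and 6. Abbreviated track: 4 weekly contacts, then month 2. The two are the same through month 2 and first differ at month 3.

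**3. Size of the difference in follow-up.**
- Length: 6 / 2 = 3.0.
- Contacts: (4 + 5) / (4 + 1) = 9 / 5 = 1.8. The difference is 4 contacts, of which months 3 and 6 carry visits.
- Total observation from Day -8, with one month = 365.25/12/7 = 4.35 weeks and the last dose in week k: (8 + 7(k − 1))/7 weeks plus follow-up. For k = 1 this is 27.2 against 9.8 weeks (ratio 2.8). For k = 7 it is 33.2 against 15.8 weeks (ratio 2.1). The factor of three therefore describes follow-up after treatment, not total time on study.

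**4. Which outcome is touched.** Two months is 2 × 4.35 = 8.7 weeks. The Section 5.3.3 outcome is read at 8 weeks post-FMT. If that is counted from the last dose, both tracks cover it. The Section 7.1 and 7.3 outcome (new SAEs or worsening of existing AEs over the study period) has no fixed end, and there the extra four months count.

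**5. Illustration of the tilt.** The documents give no dropout rate and no event rate for leavers, so both are assumed here. Take the same constant risk in both arms, with two-month risk p. The six-month risk is 1 − (1 − p)³, and if a share d of each arm leaves after the first dose, the false difference is d × [1 − (1 − p)³ − p].
- p = 10%: 1 − 0.9³ = 27.1%, a gap of 17.1 points among leavers. With d = 5% this gives 0.9 points; with d = 30%, 5.1 points.
- p from 5% to 15% and d from 5% to 30%: 0.5 to 7.1 points.

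**6. Against the margin.** Section 7.1 states 82% power for 30 per arm, a 10% rate and a 0.20 margin. This reproduces as a one-sided 0.05 calculation: SE = √(2 × 0.10 × 0.90 / 30) = 0.0775, and Φ(0.20/0.0775 − 1.645) = 82.6%. Now keep placebo at 10%, set FMT at 10% + b, and use SE = √([0.09 + (0.10 + b)(0.90 − b)]/30). The power of the test against FMT being worse is Φ((0.20 − b)/SE − 1.645): 78.0% at b = 0.9 points and 54.1% at b = 5.1 points. The last figure needs 30% of each arm to leave after the first dose.

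**The case against.** The strongest reply is that little happens in practice. The tracks are the same for two months, so no one needs the assignment at withdrawal. An unblinded pharmacist or delegate holds the randomization list and could set the track later. Every early leaver is invited to a final visit whatever the arm, and reportable events go to the DSMB on an expedited basis, so the event that prompted withdrawal would normally be judged while the blind is intact. Longer observation after donor material also fits the transmission risks described in Section 4.1.5.

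Most of this stands, and it rules out several stronger readings that a reader might infer:

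- *Everyone who leaves in the blinded phase is unblinded.* No. Leavers in the conditioning week get the abbreviated track in both arms.
- *The event behind the withdrawal is judged with the arm known.* The documents do not imply this. Only events arising or re-graded after disclosure are exposed.
- *The Section 6.1 halts are compromised.* The relatedness-based rules stop an individual's participation, which is moot for someone who has left. The study-wide halt does not use relatedness.
- *Every comparison is tilted against FMT.* The 8-week outcome is not, if counted from the last dose.

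The reply does not remove the contradiction. No section assigns the decision to the unblinded pharmacist or delays it. Even if one did, a contact at month 3 or later would tell a caller who knows the protocol that the subject had FMT. Whether it would also tell the subject depends on what subjects were told, which the text available does not show.

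**Conclusion.** The point holds in a limited form. For subjects who leave after the first enema and before the week-8 unblinding, Section 5.2.5 (with 5.2.4 and footnote 12) conflicts with Sections 4.1.4 and 6.1, and Section 5.2.3 provides no unblinding for them. Followed as written, the rule discloses the arm from about month 3, or earlier if staff are told at withdrawal. It also follows FMT leavers three times as long after treatment. Under the open-ended outcome of Sections 7.1 and 7.3 this tends to count more events on FMT.

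The real size cannot be known from the documents. The 0.9 to 5.1 points, against a margin of 20, is an illustration that assumes equal constant risk, a 10% two-month risk and 5–30% leaving after the first dose in each arm. Two readings are also assumed: FMP means active FMT product, because Section 5.2.5 contrasts it with placebo IP; and the two-month period starts at the last dose, which is not stated. This is an inexpensive correction worth making, not a fault that undermines the trial.

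**What to change.** Reconcile Sections 5.2.4, 5.2.5 and footnote 12 with Sections 4.1.4 and 6.1. For subjects who leave during the blinded phase, replace receipt of FMP as the criterion for the full track with: *at least one dose of blinded study treatment (FMT or placebo), with follow-up counted from the last blinded dose*. Both arms then share one schedule, the length and contact ratios become 1.0, and no assignment need be released to set follow-up. Keep the abbreviated track for those who leave before the first enema, where it does not depend on arm. Define FMP where it first appears. FMT recipients lose no follow-up.

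The cost is a wording change plus about four more contacts, two of them with visits, for each placebo subject who leaves after the first enema. The change does not address the separate 2- or 6-month split for completers in Section 5.2.3. That split follows planned unblinding, so it raises no disclosure problem, but it too leaves unequal follow-up.

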5.3. Assessments

5.3.1. Stool analysis

Subjects will collect a maximum of 29 stool samples over the course of the study and complete a maximum of 36 disease activity surveys. All fecal samples will be stored at -80° C. DNA will be extracted, and the V4 region of the 16S gene will be sequenced using an Illumina MiSeq (Illumina, San Diego, California) as described previously. (28) The Shannon Diversity Index will be computed for each sample and a custom python script will be used to create summary plots illustrating the relationship between clinically relevant groupings and the diversity observed in the microbiome. We will use the Shannon diversity index as our primary measure of diversity because it takes into account both abundance and evenness of species present in the community and has been shown to most robustly accommodate the variation in sampling depth. (29)

5.3.2. Microbial analysis

A long-time collaborator, [name] (MIT) and his group have pioneered novel approaches to analyzing complex microbial environments already leading to fruitful work together on IBD and the microbiome.(29) The [name] lab has a robust pipeline for processing, sequencing and analyzing this complex data and has already partnered with a leading biotechnology firm to study adult FMT for CDI. Our rich, patient-reported metadata collection technique will allow for numerous clinical correlations to be parsed out using the random forest machine learning capabilities of synthetic learning in microbial ecology (SLiME) to identify taxonomic features associated with important clinical parameters. These approaches are at the cutting edge of microbial ecology but are especially novel to the field of fecal transplantation, which has not yet been subjected to quantitative ecological analysis of any kind.

5.3.3. Clinical Outcomes

Primary Outcome Measures

- 1. Presence of FMT-related adverse events grade 2 or above.
- 2. Proportion of subjects with any FMT-related adverse events of grade 2 or above at 8 weeks post-FMT. Patient related outcomes of rectal bleeding and number of bowel movements. Rectal bleeding will be assessed using common language from PUCAI scoring. (See Figure 1)

Figure 1.

Rectal Bleeding
None
Small amount only, in less than 50% of stools
Small amount with most stools
Large amount (> 50% of stool content)

Secondary Outcome Measures

- 1. Remission as defined by PUCAI of ≤ 9
- 2. Improvement in inflammatory biomarkers (stool calprotectin, serum ESR/CRP, albumin, Hematocrit).
- 3. Changes in gut microbial composition.
- 4. Improvement of PUCAI of \geq 20 points. (30)
- 5. Assessment of engraftment of donor microbes into recipients.

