2. OBJECTIVES

2.1. Primary Objective

The primary aim of this phase I/II, randomized, placebo controlled study is the assessment of safety and tolerability of universal donor FMT compared to placebo in pediatric and young adult subjects (ages 5 years through 30 years) with Ulcerative Colitis, who have failed, are intolerant to, or have refused first-line maintenance therapy.

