7. STATISTICAL CONSIDERATIONS

7.1. Power Calculation

The primary aim of this phase I/II study is to establish whether or not FMT is a safe treatment for children and young adults with UC. Based on clinical experience, adverse events (AEs) in IBD patients are common and include abdominal pain, cramping, diarrhea, fever, bloody stool, vomiting, frequent defecation, joint pain, and eye pain. It's estimated that 70% of patients in any given year will experience a flare of their disease and have some or a combination of these symptoms. Safety, therefore, needs to be assessed relative to the high prevalence of AEs in this population. For the primary outcome, we will take any new reported SAEs or worsening of the existing AEs during the study period following enrollment into account.

The study will be powered for equivalence in the proportion of new SAEs or worsening of the existing AEs, assuming null (Ho) and alternative (Ha) hypotheses defined as follows:

$$\begin{split} & \text{Ho: } p1-p2 \leq \text{-}\delta_L \ \text{ or } p1-p2 \geq \delta_U. \\ & \text{Ha: } \delta_L \leq p1-p2 \leq \delta_U \end{split}$$

where p1 is the proportion of new SAEs or worsening of the existing AEs in the placebo group, p2 is the proportion in the FMT group, δ_L is the lower margin and δ_U is the upper margin. We expect to enroll a total of 60 patients into this study for a total of 30 FMT and 30 placebo patients. Assuming the rate of new incident SAEs or worsening of existing AEs in the placebo group is 10%, there will be 82% power to reject Ho that the difference in proportions is 0.20 or greater from zero in the same direction. Similarly, we will have an 85% power to reject a difference of 0.25 or greater if the rate of new incident SAEs or worsening of existing AEs increases to 15%.

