7.3. Data Analysis

All patients who are eligible, randomized, and have received at least one-dose of the study medication including antibiotics/placebo in the first week will be included into the analysis for primary outcomes to assess the safety and tolerability of FMT, as this will be a per protocol (and not intent-to-treat) analysis . Continuous variables will be presented as mean and standard deviation (SD) or median and interquartile range (IQR), depending on the distribution of the data. Categorical variables will be presented as number and percentage. Disease severity (PUCAI) and patient characteristics at baseline will be compared between the treatment groups to determine whether or not randomization resulted in balanced groups. Methods of 2-group comparison will include Student's t-test, the Mann-Whitney test, Pearson chi-square test, and Fisher exact test, depending on the distribution of the variable under consideration. The primary outcome of safety will be assessed via a 2×2 cross-tabulation, where the proportion of patients with new incident SAEs or upgrade of existing AEs in the FMT group will be compared to the proportion in the placebo group. Two one-sided tests for equivalence (32) will be constructed and the overall *P* value taken to be the larger of the lower and upper tests. Statistical significance will be assessed at *P*<0.05.

For the second outcome, we will use longitudinal data analysis methods to investigate changes in inflammatory biomarkers including stool calprotectin, stool lactoferrin, serum ESR/CRP, albumin, and hematocrit over the study period. Generalized Estimating Equations will be performed to examine the association between FMT and changes in these biomarkers.

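### The primary safety outcome listed in 5.3.3 is not the event or time window that 7.1 and 7.3 power and test, so the listed outcome has no expected rate, power statement or named test

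*Combined protocol and SAP*

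**What the plan says.** The primary objective (2.1) is the "assessment of safety and tolerability of universal donor FMT compared to placebo". The document then defines the primary outcome in two ways.

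- **5.3.3, Primary Outcome Measures.** Item 1 is "Presence of FMT-related adverse events grade 2 or above". Item 2 is "Proportion of subjects with any FMT-related adverse events of grade 2 or above at 8 weeks post-FMT". Rectal bleeding and number of bowel movements follow under the same item.
- **7.1.** The event that decides the primary result is described this way: "we will take any new reported SAEs or worsening of the existing AEs during the study period following enrollment into account". That sets the design: "The study will be powered for equivalence in the proportion of new SAEs or worsening of the existing AEs". The figures are 30 per arm, 82% power at a 10% placebo rate with margin 0.20, and 85% at 15% with margin 0.25.
- **7.3.** The primary safety outcome is a 2×2 table in which "where the proportion of patients with new incident SAEs or upgrade of existing AEs in the FMT group will be compared" with placebo, using two one-sided tests (TOST) at 0.05.

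No section maps one definition to the other, ranks them, or says that one is descriptive and the other inferential.

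**The concern.** Section 5.3.3 requires a minimum grade and attribution to FMT, but not seriousness. Sections 7.1 and 7.3 require seriousness or a change from an existing AE, but neither grade nor attribution. An analyst following 5.3.3 and one following 7.3 would fill different 2×2 tables from the same 60 patients, and each could call the result primary.

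The comparison of safety and tolerability with placebo is the purpose of the trial. If the definition is still open when results by arm become visible, the choice can be made with knowledge of the answer. The power statement would also be read as applying to an outcome for which it was not calculated.

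**Working it through.** **1. The definitions side by side**

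| Feature | 5.3.3 | 7.1 / 7.3 |
|---|---|---|
| Grade 2 or above required | yes | no |
| Attribution to FMT required | yes | no |
| Seriousness, or worsening of an existing AE, required | no | yes |
| Window | 8 weeks post-FMT | study period after enrollment (7.1); none given in 7.3 |
| Expected rate and power | none | 10% / 82%; 15% / 85% |
| Named primary test | none | TOST |

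**2. Does either contain the other?**

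| Patient has | 5.3.3 | 7.1 / 7.3 |
|---|---|---|
| New, non-serious grade 2 fever judged FMT-related | counts | does not count |
| SAE judged unrelated | does not count | counts |
| Existing AE upgraded, judged unrelated | does not count | counts |
| New SAE of grade 2 or above judged FMT-related | counts | counts |

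The events overlap, but neither is a subset of the other.

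**3. Windows.** Under 5.2.3, placebo subjects who have not improved after the blinded 8 weeks may receive open-label FMT. Read literally, the 7.1 window continues into that period, so events occurring on FMT could be counted in the placebo arm. Counted from the first dose, the 5.3.3 window would largely avoid this.

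**4. The plan's power figures.** Inputs from 7.1 and 7.3: n = 30 per arm, equal true rates p, margin m, 0.05 per one-sided test.

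SE = √[2p(1−p)/30]; power of one one-sided test = Φ(m/SE − 1.645).

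- p = 0.10, m = 0.20: SE = 0.0775; Φ(2.582 − 1.645) = 82.6% (stated 82%).
- p = 0.15, m = 0.25: SE = 0.0922; Φ(2.712 − 1.645) = 85.7% (stated 85%).

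Both reproduce, for the 7.1 event and as the power of one of the two one-sided tests. Passing both tests, as 7.3 requires, has power of about 2Φ(m/SE − 1.645) − 1, which is 65% and 71%. That gap is a separate point. It is noted here because the figures in step 6 are for both tests.

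**5. Can the two definitions disagree?** The counts are assumed; the margin of 0.20 is from 7.1. Suppose 3 subjects per arm have an SAE or upgraded AE, all judged unrelated. In addition, 8 FMT and 1 placebo subjects have a new, non-serious grade 2 AE judged related.

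- 7.3 event, 3/30 v 3/30: difference 0, SE = 0.0775, 90% CI −12.7 to +12.7 points. z = 0.20/0.0775 = 2.58, TOST P = 0.005: equivalence concluded.
- 5.3.3 event, 8/30 v 1/30: FMT excess 26.7% − 3.3% = 23.3 points. SE = √(0.2667×0.7333/30 + 0.0333×0.9667/30) = 0.0871, 90% CI 9.0 to 37.7. z = (0.20 − 0.2333)/0.0871 = −0.38, TOST P = 0.65: equivalence not shown. Fisher two-sided P = 0.026 against FMT.

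**6. Does the stated power carry over?** Only if the chosen event also has a placebo rate near 10% (margin 0.20) or 15% (margin 0.25). With 30 per arm, power to pass both tests is:

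| True rate in both arms | Margin 0.20 | Margin 0.25 |
|---|---|---|
| 10% | 65% | 89% |
| 15% | 40% | 71% |
| 20% (assumed) | 23% | 56% |

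The documents give no rate for the 5.3.3 event.

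**The case against.** **The sections have different roles: 5.3.3 is descriptive and 7.3 inferential.** That would be a reasonable arrangement, but the document does not state it and labels both primary. The general two-group methods in 7.3 follow the sentence on baseline balance. The only event named for the primary test is the SAE-or-upgrade event.

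**Harm would not be hidden.** This stands. A reader might infer that an excess of related reactions could go unseen. However, the 5.3.3 proportion remains a listed outcome, and 6.1 sends unexpected grade 2 or higher AEs that are possibly or probably FMT-related to the DSMB on an expedited basis. The gap is in the formal test.

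**Many FMT reactions would count under 7.1 anyway.** This partly stands. Section 7.1 lists abdominal pain, diarrhea and fever as common in this population, so some reactions would register as worsening of an existing AE. What escapes the 7.3 test is the new, non-serious event.

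**The conflict rests on invented counts.** Correct. Section 4.1.5 describes transient fever and abdominal pain after FMT but gives no rate. The example shows possibility only.

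**An all-cause composite is not the obvious cure.** This also stands. Nothing in the documents requires one, and 7.1's own figure of 70% flaring in a year suggests a high rate. At a constant hazard, 1 − 0.30^(8/52) is about 17% in 8 weeks, before any other AE is counted.

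**The rectal bleeding and bowel movement text may be a run-on list item.** Possibly. It sits under the primary heading, but it is the weakest part of the point.

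**Conclusion.** The inconsistency is real and needs correction. The listed primary outcome and the powered and tested one differ in relatedness, grade, seriousness and window, and nothing in the document reconciles them. The outcome in 5.3.3 therefore has no expected rate, power statement or named test.

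Three stronger readings are not supported. A reader might infer that the trial will give opposite safety answers, but the documents give no event rates from which to predict that, and the two events can overlap. A reader might infer that the mismatch makes the 82% and 85% arithmetically wrong, but they reproduce for the 7.1 event as a single one-sided test; what fails is carrying them over to 5.3.3. A reader might infer that one of the two events is the correct primary, but the documents do not settle that.

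The set comparison rests only on the wording of the three sections, reading the absence of a relatedness condition in 7.1 and 7.3 as meaning that none applies. The power figures assume equal true rates, the normal approximation and no dropout.

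**What to change.** - Name one primary safety event and one window confined to the randomized, blinded 8 weeks, and state it in identical words in 5.3.3, 7.1 and 7.3. The choice of event is the sponsor's.
- Make the other definition, rectal bleeding and stool number secondary.
- Restate the placebo rate, margin and power for the chosen event, with power calculated for both one-sided tests.
- Align 6.1. It limits recording to AEs meeting its reporting criteria, under which grade 2 events qualify only if unexpected and possibly or probably FMT-related. That would omit expected related grade 2 AEs (part of 5.3.3) and unrelated worsening below grade 3 (part of 7.1 and 7.3). Section 8 describes a running AE log entered on case report forms, so the document should say which rule governs.
- Do this before any unblinding. Section 5.2.3 unblinds each subject after the week 8 dose, so waiting for the end of the study would be too late.

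**Cost.** Changes to wording and AE data capture; no extra visits are needed to settle the definition. The restated power may be clearly lower for a broader event. At margin 0.20 it falls from about 65% at a 10% rate to 40% at 15% and 23% at an assumed 20%, so sample size or margin might then need to be revisited.
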